APPENDIX 2: SCHEDULE OF ASSESSMENTS

	Pre-Procedure	Post-Op Day 1	Optional Post-Op Days 2-10	Optional Post-Op Month 1-2	Post-Op Month 3 (60-120 Days)	Post-Op Month 6 (150-180 Days)	Optional Post-Op 1 Year	Optional Post-Op 2 Year	Optional Post-Op 3 Year
Informed Consent	X								
Demographics	X								
Medical History/Concomitant Medications	X			X ³	X	X	X	X	X
Contact Lens History	X			X ³	X	X	X	X	X
History of Prior Eye Surgery	X								
Slit Lamp Exam	X	X	X	X	X	X	X	X	X
Fundus Exam	X ¹								
Intraocular Pressure (IOP)	X	X ³	X	X	X	X	X	X	X
Uncorrected Visual Acuity (UCVA)	X	X	X	X	X	X	X	X	X
Corrected Distance Visual Acuity (CDVA)	X	X ³	X ³	X ³	X	X	X	X	X
Manifest Refraction	X	X ³	X ³	X ³	X	X	X	X	X
Pachymetry	X ²	X ³	X ³	X	X ²	X	X	X	X
Pentacam Corneal Topography/Tomography	X	X ³	X ³	X	X	X	X	X	X
Quality of Life Survey	X ³				X ³	X ³	X ³	X ³	X ³
Prior Eyeglass Prescriptions, UCVA, CDVA, and Topographic Maps	X ³								
Other Optional Assessments	X ⁴	X ⁴	X ⁴	X ⁴	X ⁴	X ⁴	X ⁴	X ⁴	X ⁴

¹OR DOCUMENTED DILATED FUNDUS EXAM BY ANOTHER PROVIDER

²BY ULTRASOUND OR OTHER SCANNING DEVICE SUCH AS PENTACAM

³OPTIONAL ASSESSMENT PROCEDURES

⁴OTHER ASSESSMENTS INCLUDE CORNEAL WAVEFRONT, OPTICAL COHERENCE TOMOGRAPHY (OCT), BRILLOUIN MICROSCOPY, ITRACE WAVEFRONT ABERROMETRY/TOPOGRAPHY, ORBSCAN CORNEAL TOPOGRAPHY, TOMOGRAPHY, CONTRAST SENSITIVITY TESTING, OR OTHER NON-INVASIVE DIAGNOSTIC TOOLS THAT MAY BE AVAILABLE TO AN INVESTIGATOR.

[figure not shown]
APPENDIX 3: UVA LIGHT CALIBRATION, CENTERING, AND APPLICATION INSTRUCTIONS

UVA Light Calibration, Centering, and Application Instructions to Ensure Safe UVA Treatment

[figure not shown]
NOTE: Please read the CXLUSA UVA Illumination System User’s Manual prior to initiating clinical use. No patient is to be treated with UVA unless adequate corneal stromal riboflavin loading has been confirmed by slit lamp examination using the grading system defined in the Study Flip Chart.

The UVA study device has a fixed, non-adjustable aperture. To achieve consistent 12 mm diameter circular UVA beam (for either 4 or 6 mW/cm² treatment) the following steps must be performed prior to every cross-linking procedure.

1. Put on a pair of safety glasses supplied with the UVA Illumination System.
2. Turn ON the UVA Illumination Source, and allow 10 minutes for warm-up prior to calibration.
3. Draw a 12 mm diameter circle on a white piece of paper.
4. Place the external radiometer on a solid surface (cart, counter-top, etc.).
5. Place the white piece of paper on top of the external radiometer.
6. Set the Shutter Select Switch on the front of the UVA illumination source to “Open”.
7. Set the selector on the front of the Power Control Box mounted on the pole with caster base to “Single,” to limit UVA output to the left emission aperture only.
8. Swipe a “Calibration” magnetic card through the card reader to activate UVA illumination and confirm that the UVA light is on by observing a bright white spot on the white piece of paper.
9. Adjust the distance from the left emission aperture optic to the paper until the beam spot size is the same as that of the 12 mm diameter circle, and record this distance.
10. Remove the paper from the top of the radiometer, and by moving the radiometer from side-to-side, verify that the 12 mm beam encompasses the entire area of the 9 mm diameter radiometer sensor. This assures that the radiometer will accurately measure UVA irradiance and that the UVA device will be properly calibrated.

Incorrect

[figure not shown]
Correct

9 mm diameter
radiometer sensor
covered by 12 mm
diameter UVA beam

[figure not shown]

11. Turn the knob on the Intensity Adjustment box mounted on the pole with caster base clockwise/counterclockwise to adjust the UVA output to the desired irradiance (e.g. 4 or 6 mW/cm²).
12. If simultaneous, bilateral corneal cross-linking will be performed, turn the selector switch on the front of the Power Control Box to “Dual”. Note that the LED on top of the control box is illuminated.
13. Repeat calibration steps above to calibrate the right UVA emission aperture.
14. After completion of calibration procedures, re-swipe the Calibration card to close the illumination source shutter.
15. Ensure the patient is lying down in a comfortable position. Provide a pillow for their back or neck if needed to ensure comfort and reduce movement during the treatment. Instruct the patient to remain in this position without moving their head and, when necessary, repeat these instructions to avoid movement during the procedure.
16. For treatment, position the UVA optic at the distance from the cornea that was previously measured to create a 12 mm diameter circle. This consistently provides a 12 mm UVA beam spot size.
17. Swipe a Treatment card labeled with the Randomization Group to which the patient has been randomized.
18. Center the beam on the cornea. This is easily performed since the UVA beam spot size is easily delineated by bright fluorescence of the riboflavin-loaded cornea, assuring for easy and consistent beam centration. Use this fluorescence and easy visibility of the beam to confirm accurate positioning at the initiation UVA illumination, and throughout the Treatment procedure.

If the patient moves, you will see the beam is off center. The image below shows a decentered beam that can be seen to not sufficiently cover the cornea (right yellow arrow) and to be decentered onto the eyelid (left yellow arrow). During the UV procedure, the centration is monitored in this fashion in each eye. In this image, no speculum has been placed. In the current study, speculae will be placed which will also assist in centration and placement of the UVA beam making these even more accurate and safer.

Beam Properly Centered

Beam Off Center

19. Monitor the patient's cooperation and eye position during the dark cycle of treatment i.e. when the UVA light has been turned off by the illumination source shutter. If the patient tends to look away from the optic, this is obvious and the patient should be instructed to look straight ahead again.
20. Be aware also of the cadence of UVA light turning on and off at consistent 15-second intervals. This is easily monitored by observation of the light turning on and off and by the audible sound of the illumination source shutter opening and closing.
21. To ensure optimum accuracy and precision in calibration, radiometers should be replaced 12 months after receipt.

1. INTRODUCTION

CXL intends to utilize data from the ongoing CXL-005 Phase 2 clinical study to support the design of a Phase 3 trial. In preparation for a meeting with the FDA to propose the Phase 3 design, interim data from CXL-005 will be analyzed to help design the Phase 3 protocol. This version of the SAP describes the analyses planned to support the meeting with FDA.

This SAP is based on Version 4.3 of the study protocol dated 05-May-2017. Should the SAP and the protocol be inconsistent with respect to the planned analyses, the language of the SAP is governing. All analyses will be conducted using SAS version 9.4.

1.1 Study Design

Approximately 3,000 eligible subjects presenting with asymmetric corneas will be enrolled at 21 clinical sites.

The planned primary effectiveness analysis will be based on 6-month post-procedure assessments. Subjects will be assessed post-procedure day 1, at 3 months and at 6 months. Visual acuity measurements and full ocular assessments (manifest refraction with CDVA, UCVA, slit lamp biomicroscopy including a rating of corneal haze, pachymetry, Pentacam corneal tomography, IOP) will be performed during that period.

According to the protocol, Optional 1 week, 1-2 month, 12-month, 24-month, and 36-month assessments will also be performed, at the discretion of the physician. The 1-2 month visit may occur if the subject experiences changes in refractive error, and requires a new prescription for spectacles or contact lenses.

In order to provide 12-month data to FDA for Phase 3 planning, sites were instructed to contact patients to request a 12-month assessment. In these cases, patients may have a 6-month visit that suggests they completed study, yet still return for the 12-month assessment. Not all patients that completed study at the 6-month visit will return for a 12-month assessment.

1.1.1 Randomization

Randomization will be stratified by indication and by investigational site among 3 UVA illumination groups consisting of:

Group 1	4 mW/cm ² cycled On/Off at 15 second intervals for 20 minutes (total UVA corneal surface dose of 2.4 J/cm ²)
Group 2	6 mW/cm ² cycled On/Off at 15 second intervals for 20 minutes (total UVA corneal surface dose of 3.6 J/cm ²),
Group 3	4 mW/cm ² cycled On/Off at 15 second intervals for 30 minutes (total UVA corneal surface dose of 3.6 J/cm ²)

1.2 Study Objectives

The objectives of the study are to assess changes in visual acuity and corneal symmetry after corneal collagen cross-linking (CXL) of asymmetric corneas.

1.2.1 Primary Objectives

The primary objective of this study is to assess change in corrected distance visual acuity (CDVA) at months 6 and months 12 using Snellen converted to the LogMAR scale.

1.2.2 Secondary Objectives

The secondary objectives of this study are:

- To assess the change in uncorrected distance visual acuity (UCVA) at months 6 and months 12 using Snellen converted to the LogMAR scale
- To assess change in K_{\max} at months 6 and months 12.

1.3 Endpoints

1.3.1 Primary Efficacy Endpoint

The primary efficacy endpoint is the LogMAR of CDVA as defined by:

$$\text{LogMAR} = -\text{Log} \left[\frac{20}{(\text{Snellen Acuity per CRF})} \right]$$

where the log base 10 is used. The usual adjustment for the number of letters read is omitted from the conversion formula since the number of letters read was not captured.

1.3.2 Secondary Endpoints

Secondary endpoints include change from baseline in the following assessments:

- LogMAR of UCVA
- K_{\max}

1.3.3 Safety Endpoints

The safety endpoints for this analysis include frequency, intensity, and relationship to study drug of adverse events and serious adverse events.

1.4 Determination of Sample Size

Three thousand subjects will be enrolled in this open-label, prospective multicenter trial. One or both eyes of each patient may be enrolled and evaluated, based on whether treatment is unilateral or bilateral, based on clinical indications. All eyes treated (single or both eyes of an individual subject) will be included in the analysis of safety and efficacy. Additional details regarding the sample size for the study can be found in the protocol.

The sample size for this ad hoc analysis is partially driven by the enrollment date. All patients with at least one procedure performed are included in the safety analysis. Only patients with a diagnosis of keratoconus, who do not have prior conductive keratoplasty treatment, who are in the study long enough to be eligible for a Month 12 visit are considered for inclusion in the efficacy analysis. Additional details regarding the subset of patients for efficacy analysis can be found in Section 3.2.2

1.5 Timing of Analysis

Analyses will be performed after the interim database lock. The official data for the analysis will be based on SAS datasets subset to include patients eligible for this analysis.

1.6 Changes from Protocol

The protocol states the primary efficacy endpoint of this trial is change in corrected distance visual acuity (CDVA) at the last required study visit (6 months post-op), compared to baseline. For this analysis, the change in CDVA will be estimated at Month 6 as well as Month 12.

The protocol also states that two-sample t-tests will be used for treatment comparisons. Since there are three treatment groups, analysis of variance (ANOVA) will be used instead of conducting separate t-tests on each pairwise combination of treatments. Separate t-tests on each pairwise comparison will be performed as a supportive analysis.

2. DATA

The protocol states that patients complete study at Month 6, and subsequent visits are optional. In planning for the FDA meeting, sites have been instructed to request the Month 12 visit.

2.1 Filtering

Data to be presented in the efficacy analysis are limited to a subset of patients as defined in Section 3.2.3. Filtering will only be done on efficacy data. Baseline and safety data will include all patients randomized and treated as of the data lock date.

Due to database limitations, randomization date is assumed to be the date of the first procedure as determined by the visit date for the Procedure Visit.

Some patients will have longer follow-up data than others. Filtering will not attempt to exclude data from beyond the Month 12 visit. All safety data will be used, but efficacy data beyond Month 12 CRF page will not be analyzed.

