6.3 ANTICIPATED ADVERSE EVENTS

Epithelial Defect – A breach in the corneal epithelium that does not heal within 24 hours.

Persistent Epithelial Defect - A breach in the corneal epithelium that does not heal within 2 weeks.

Significant Decrease in Visual Acuity – loss of ≥ 2 lines CDVA

Sterile Infiltrates – Gray-white lesions caused by acute immune response to corneal damage.

Central Stromal Scars – New, significant corneal opacity in the central stromal region.

Corneal Haze – Cloudy or opaque appearance of the cornea. Grade Scale: 0 = clear cornea; 1 = focal areas of minimal stromal clouding or reticulation; 2 = diffuse mild stromal clouding or reticulation; 3 = Diffuse stromal clouding or reticulation somewhat obscuring the iris details; 4 = focal or diffuse areas of dense stromal haze obscuring iris detail.

Infectious Keratitis – Microbial infection of the epithelium or stroma.

Corneal Melt – A progressive, rapidly expanding, erosive, non-infectious, corneal ulcer.

Non-Infectious Keratitis – Inflammation of the cornea not associated with an infection.

Eye Pain – Eye pain lasting for >5 days.

Conjunctiva Hyperemia – Eye redness.

Foreign Body Sensation – Patient reports a feeling of a foreign body (e.g. gravel or sand) in the eye lasting >24 hours.

Corneal Hydrops – Acute corneal edema caused by a break in Descement membrane.

Herpes Simplex Virus (HSV) Reactivation – Epithelial keratitis, stromal keratitis, or disciform edema proven or clinically diagnoses as being caused by HSV.

Disease progression – Increase of $\geq 4D K_{max}$ as assessed by topography or tomography or loss of > 2 lines of CDVA.

Photophobia – Sensitivity to light lasting > 24 hours.

Elevated Intraocular Pressure (IOP) – IOP ≥ 30 mmHg or an increase in IOP of ≥ 10 mm from baseline recorded on two separate occasions or an increase in IOP that requires intervention.

Dry Eye Syndrome (DES) – Irritation of corneal surface due to inadequate production of tears that is consistently worse than the patient's pre-procedure state longer than 3 months after the cross-linking procedure.

Endophthalmitis – Diffuse intraocular inflammation predominantly involving the vitreous cavity but also involving the anterior chamber, implying a suspected underlying infectious cause.

Iritis – Presence of inflammatory cells in the anterior chamber. The presence of aqueous flare alone is not considered to constitute iritis.

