8.3 SAFETY

AEs, SAEs, and other findings will be summarized by presenting the percentages of subjects with each event. Continuous endpoints will be summarized using summary statistics such as means, medians, standard deviations, minima, maxima, and relevant percentiles.

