3.2.2 Safety

The safety analysis set (SS) includes all subjects enrolled in the treated analysis set. Safety analysis will be performed using the Safety Analysis Set. Analysis of the SS will be performed by the treatment actually received as recorded on the CRF. Subjects with initial unilateral treatment that have a subsequent procedure may appear in the SS under different treatment groups if the subsequent treatment differs from the initial treatment.

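### The interim adverse event percentages cover no defined period of follow-up, and dry eye syndrome is understated as a result

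*SAP*

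**What the plan says.** SAP 1 describes an interim analysis of an ongoing Phase 2 study, made to support a meeting with FDA and the design of a Phase 3 trial.

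**Who is counted.** For safety, SAP 2.1 says "Baseline and safety data will include all patients randomized and treated as of the data lock date", SAP 1.4 says "All patients with at least one procedure performed are included in the safety analysis", and SAP 3.2.2 says "The safety analysis set (SS) includes all subjects enrolled in the treated analysis set". None of these sets a minimum follow-up. For efficacy, SAP 1.4 admits only patients "who are in the study long enough to be eligible for a Month 12 visit are considered for inclusion in the efficacy analysis", and SAP 2.1 confirms that "Filtering will only be done on efficacy data".

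**What is reported.** Protocol 8.3 plans to summarize adverse events by "presenting the percentages of subjects with each event". SAP 3.1 plans counts and percentages, and SAP 6.1.1 counts each term once per subject.

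**How time is handled.** SAP 2.1 acknowledges that "Some patients will have longer follow-up data than others", and then uses all safety data, including data from after Month 12. SAP 6 and the table list in Appendix B contain no summary of follow-up time, no rate for a fixed period and no time-to-event estimate. The disposition summary (SAP 4.1, Table 1) counts subjects who are ongoing, completed or discontinued, and Listing 1 gives procedure dates.

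**The event that needs time.** Protocol 6.3 requires dry eye syndrome to be "consistently worse than the patient's pre-procedure state longer than 3 months after the cross-linking procedure".

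**The concern.** A percentage of subjects with an event can be read as a risk only if the reader knows over what period. Here the denominator mixes subjects treated just before the lock with subjects who came back at one year or later. The numerator takes events from any time after the procedure.

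For dry eye syndrome the problem has a known direction. A subject with 3 months of follow-up or less cannot meet the protocol definition, yet is counted in the denominator. What is at stake is the absolute rate carried into Phase 3 planning and the FDA meeting, more than the comparison of the three UVA groups.

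**Working it through.** The documents give no adverse event rate, no size of the safety set at the lock, no lock date and no accrual curve. There is therefore no planned figure to reproduce, and the sizes below are illustrations. The SAP does not write out the adverse event denominator; it follows from the safety set definition together with percentages of subjects.

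**1. Dry eye, by definition.** Let *s* be the share of the safety set with 3 months of follow-up or less, and *p* the proportion with dry eye among subjects followed longer. The first group contributes no events, so

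printed percentage = *p* × (1 − *s*).

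The relative understatement equals *s*. It is zero only if everyone was followed past 3 months.

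**2. Size of *s*.** Assume uniform accrual over *A* months up to the lock, so that *s* = 3/*A*, and assume *p* = 10%.

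- *A* = 24: *s* = 3/24 = 12.5%; printed 10% × 0.875 = 8.75%.
- *A* = 36: *s* = 3/36 = 8.3%; printed 10% × 0.917 = 9.2%.

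Subjects lost within 3 months of their procedure would add to *s*.

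**3. Later detection.** The required Month 3 visit may fall between day 60 and day 120 (protocol 5.4), so it can come before the definition can be met. If dry eye were found only from the opening of the Month 6 window at day 150 (about 5 months), *s* = 5/*A*.

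- *A* = 24: *s* = 20.8%; printed 7.9%.
- *A* = 36: *s* = 13.9%; printed 8.6%.

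**4. Why 24 to 36 months.** The revision that introduced randomization is dated 2 October 2014, and the SAP cites a protocol dated 5 May 2017. These are about 31 months apart. At *A* = 31, *s* = 3/31 = 9.7% and the printed value is 9.0%. Neither date is a first treatment or a lock, so the range remains an assumption.

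**5. Other anticipated events.** The other durations named in protocol 6.3 run from 24 hours to 2 weeks. For 2 weeks (0.46 months) and *A* = 24, *s* = 0.46/24, about 2%, so the effect is small.

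**6. The direction can reverse against a fixed period.** Take an event with 5% risk by Month 12 and onset spread evenly from Month 3 to Month 12. Its Month 6 risk is 5% × 3/9 = 1.67%. Under uniform accrual over 24 months:

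- if follow-up stops at Month 6, the crude percentage is (2.5 + 18 × 1.67)/24 = 1.35%, below 1.67%;
- if everyone is followed to the lock, it is (22.5 + 12 × 5)/24 = 3.44%, above 1.67%.

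The true mix lies between these cases, because post-Month 6 visits are optional. The crude figure therefore cannot be read as a Month 6 risk.

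**The case against.** The strongest reply is that percentages over all treated subjects are the usual safety display, that this analysis is ad hoc and interim, and that Table 1 and Listing 1 already show who has not completed Month 6. Much of this stands, and the all-treated tables should stay. But disposition counts are not follow-up times, and they leave the adverse event percentages unchanged. The descriptive-only statement in SAP 3.2.3.1 concerns efficacy.

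A second reply is that even dry eye is not fully excluded early. Tables 7.2 and 7.3 use coded terms, and SAP 6.2 takes anticipated status from a CRF field alone, so neither table applies the 3-month threshold. An early dry-eye complaint could be coded and counted. This is fair, and it would make the understatement smaller than the formula gives.

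A reader might go further than the documents allow in three ways.

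- **That CDVA loss, haze and raised IOP also cannot be counted early.** Protocol 6.3 sets no minimum elapsed time for them. Events are collected from the day of the procedure (protocol 6.0), a slit lamp examination is required on Day 1, and unscheduled visits for adverse event follow-up are recorded (protocol 5.4).
- **That dilution could be as high as 42%, turning 10% into 5.8%.** That takes 12 months of accrual and detection only from day 150. With uniform accrual over 12 months, the share with 12 months of follow-up is (12 − 12)/12, or zero, which would leave almost nobody eligible for Month 12 efficacy under SAP 1.4. At 24 and 36 months the share is 50% and 67%.
- **That the arm comparison is biased.** Concurrently randomized arms should have similar follow-up.

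**Conclusion.** The point holds in a limited form. The planned percentages correspond to no defined risk period. Dry eye syndrome, as the protocol defines it, is understated relative to subjects followed past 3 months, by the share of the safety set with less follow-up than that. Under the assumed 24 to 36 months of uniform accrual, the relative understatement is about 8% to 12.5%, or 14% to 21% if detection waits until day 150. The 10% rate and the accrual pattern are assumptions, and the true size cannot be derived from the documents.

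A reader might infer that all adverse event rates are too low. The documents do not support that: because events are counted without an upper time limit, a rate may be above or below the Month 6 risk.

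The SAP cites protocol version 4.3 and the protocol to hand is an earlier revision, so the dry eye definition should be confirmed in 4.3. This is a cheap improvement to the reporting and does not invalidate the analysis.

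**What to change.** Keep the all-treated tables. Add to SAP 6 and Appendix B:

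1. A summary by arm of follow-up time since the procedure. For a subject with a later procedure in another group, state which procedure starts the clock.
2. Tables 7.2 and 7.3 repeated for events with onset up to the end of the Month 6 window. The denominator is all subjects whose procedure date is far enough before the lock for that window to have closed, whether or not they stayed in the study. For dry eye, a Kaplan-Meier Month 6 proportion is an alternative, with the event timed when the definition is met.

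First reconcile the Month 6 window, which is 150-210 days in protocol 5.4 and 150-180 days in protocol Appendix 2. Flag events with an imputed onset date: SAP Appendix C sets a fully missing onset to the first treatment date, which would place the event at time zero.

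Two alternatives are best avoided. A rate per patient-month would dilute dry eye again, because the first 3 months carry no risk by definition. A denominator of those who reached day 150 or ended the study earlier would keep recent early leavers while dropping their ongoing peers.

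The cost is a SAP text change and a few tables. Procedure dates are already planned for Listing 1. The downsides are smaller denominators, some higher stated rates, and reliance on onset dates that are sometimes missing; the requirement to record them came only with Revision 03 in November 2015.
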